3.5 VISIT SCHEDULE

The Week 12 visit for the pivotal studies NI-AC301 or NI-AC302 will serve as the Baseline Visit for this long term safety study. Subjects must have completed the full 12 weeks of treatment in one of the pivotal studies to enroll in the long term safety study. Subjects may enter the long term safety study up to 7 calendar days after their Week 12 visit in the pivotal study. Study visits will take place after the first four weeks then at Weeks 4, 12, 24, 36 and 40.

3.6 STUDY POPULATION

Approximately 600 healthy male and female subjects with acne vulgaris on the face, chest, shoulders or back will be allowed to participate in the study if they have successfully completed 12 weeks in either NI-AC301 or NI-AC302.

A subject whose facial acne cleared during NI-AC301 or NI-AC302 is eligible to enroll if all other inclusion criteria and none of the exclusion criteria are met. If a subject enters the pivotal study at age 40 and is 41 at the time they complete participation in the pivotal study, they are eligible for the long term safety study as long as they meet all other study inclusion criteria and none of the exclusion criteria.

3.7 ELIGIBILITY CRITERIA

3.7.1 INFORMED CONSENT AND AUTHORIZATION TO RELEASE HEALTH INFORMATION

Written informed consent/assent will be obtained from all subjects before any study-related procedures are performed. The Investigator may discuss the study and the possibility for entry with a potential subject without first obtaining consent/assent. A subject wishing to participate must give written informed consent/assent prior to any study-related procedures being conducted. The Investigator has both the ethical and legal responsibility to ensure that each subject being considered for inclusion in this study has been given a full explanation of the procedures and expectations for study participation. The Week 12 assessments for the pivotal study NI-AC301 or NI-AC302 should be done prior to consenting the subject for participation in this long term safety study.

The site-specific informed consent and assent forms must be forwarded to Chiltern for approval prior to submission to an Institutional Review Board (IRB) as appropriate. Each subject will sign the consent form that has been approved by the same IRB responsible for protocol approval. Each informed consent document must adhere to the ethical principles stated in the Declaration of Helsinki and will include the elements required by the Food and Drug Administration (FDA) regulations in 21 CFR as well as the International Conference on Harmonisation (ICH) Good Clinical Practice (GCP) guidelines, and applicable federal and local regulatory requirements. The consent form(s) must also include a statement that Novan, Chiltern (or their designees) and auditing regulatory agencies will have direct access to the subject's records and medical history.

Once the appropriate essential information has been provided to the subject and parent or legal guardian (where applicable) and fully explained by the Investigator (or a qualified designee) and it is felt that the subject understands the implications and risks of participating in the study, the IRB approved consent and assent (where applicable) document(s) shall be signed and dated by both the subject and parent or legal guardian (where applicable) and the person obtaining consent (Investigator or designee), and by any other parties required by the IRB or other regulatory authorities. A subject under 18 years of age (or the age of majority in their state) must sign a written informed assent and be accompanied by the parent or legal guardian at the time of consent/assent signing. If a subject becomes 18 years of age during the study, the subject must provide written informed consent at the next study visit to continue study participation. The subject will be given a copy of the signed informed consent document with the original kept on file by the Investigator. All of the above activities must be completed before any study related procedures are conducted.

3.7.2 INCLUSION CRITERIA

Each subject must fulfill all of the following inclusion criteria to participate in the study:

- 1. Have a signed written informed consent form. Subjects less than 18 years of age or the age of majority in their state must sign an assent form for the study and a parent or a legal guardian must sign the informed consent;
- 2. Have completed the full 12 weeks of treatment in NI-AC301 or NI-AC302;
- 3. Be in good general health;
- 4. Have no more than two nodules or cysts on the face;
- 5. Women of childbearing potential (WOCBP) must have a negative urine pregnancy test (UPT) prior to enrollment;
- 6. WOCBP must agree to use an effective method of birth control during the course of the study and for 30 days after their final study visit;
- 7. Be willing and able to follow study instructions and likely to complete all study requirements. Subjects under 18 years of age or age of majority must be accompanied by the parent or legal guardian at the time of assent/consent signing.

3.7.3 EXCLUSION CRITERIA

Subjects will not be enrolled if they meet any of the following exclusion criteria:

- 1. Have any dermatological conditions on the face that could interfere with clinical evaluations such as acne conglobata, acne fulminans, acne secondary to medications or other medical conditions, perioral dermatitis, clinically significant rosacea, or gram-negative folliculitis;
- 2. Have any underlying disease(s) or some other dermatological condition of the face that requires the use of interfering topical or systemic therapy or makes evaluations and lesion count inconclusive;
- 3. Have an on-going adverse event at the Week 12 visit for NI-AC301 or NI-AC302 that warrants stopping study drug application;
- 4. Are transgender persons who are taking testosterone (female to male) or estrogen (male to female);
- 5. Have facial hair, tattoos or other markings that could interfere with assessments or application of study drug;
- 6. Have a history of experiencing significant burning or stinging when applying any facial treatment (e.g., make-up, soap, masks, washes, sunscreens, etc.) to their face;
- 7. Female subjects who are pregnant, nursing mothers, or planning to become pregnant during the study;

- 8. Intend to use a tanning booth or sunbathe during the study;
- 9. Are members of the same household where a subject is enrolled in NI-AC301, NI-AC302, or NI-AC303;
- 10. Are immediate family members of study site personnel directly involved in NI-AC301, NI-AC302, or NI-AC303;
- 11. Have any condition or situation which, in the Investigator's opinion, puts the subject at significant risk, could confound the study results, or may interfere significantly with the subject's participation in the study;
- 12. Are unable to communicate or cooperate with the Investigator due to language problems, poor mental development, or impaired cerebral function;
- 13. Concurrently participating in a different interventional research study.

4. STUDY PROCEDURES AND METHODS

4.1 SUBJECT ENTRY PROCEDURES

Prospective subjects as defined by the eligibility criteria in Sections 3.7.2 and 3.7.3 (Inclusion/Exclusion Criteria) will be considered for entry into this study. Subjects' informed consent/assent must be obtained prior to conducting any procedures for this study and after completion of the Week 12 assessments for NI-AC301 or NI-AC302.

Some baseline procedures (i.e., review of inclusion/exclusion criteria, brief physical exam, blood pressure and pulse rate, lesion counts, cutaneous tolerability, adverse event assessment, concomitant medication review and UPT) must be completed prior to dispensing open label study medication.

WOCBP having a positive UPT at baseline may not be randomized into the study. Women of childbearing potential must agree to use an effective form of contraception during participation in the study and for 30 days after their final study visit. Effective contraception is defined as stabilized on oral contraceptive for at least three months (90 days), intrauterine device (IUD), condom with spermicide, diaphragm with spermicide, implant, NuvaRing®, medroxyprogesterone injection, transdermal patch or abstinence with a documented second acceptable method of birth control should the subject become sexually active. Females taking hormonal contraceptives must have taken the same type for at least three months (90 days) prior to entering the study and must not change type during the study. Subjects who had used hormonal contraception and stopped must have stopped no less than three months prior to the start of the study.

A female is considered to be of childbearing potential UNLESS she is post-menopausal (no menses for 24 consecutive months), surgically sterilized, or without a uterus and/or both ovaries. Premenarchal girls are considered to be of childbearing potential.

After the required procedures are completed and study eligibility is confirmed, study drug will be dispensed to the subject. The subject will be trained on the mixing, application, and storage of the study drug. All study drug applications will be done at home.

Table 2: Schedule of Visits and Procedures

Study visits should occur at approximately the same time of day throughout the study.

PROCEDURES	Visit 1 ¹ Baseline (Day 0)	Visit 2 ³ Week 4 ±5 days (Day 28)	Visit 3 Week 12 ±7 days (Day 84)	Visit 4 Week 24 ±7 days (Day 168)	Visit 5 Week 36 ±7 days (Day 252)	Visit 6 ⁴ Week 40/ET ±7 days (Day 280)
Informed Consent/Assent	X					
Demographics	X^2					
Medical History	X					
Medication History	X					
Inclusion/ Exclusion Criteria	X					
Brief Physical Examination	X^2					X
Urine Pregnancy Test (all WOCBP)	X ²	X	X	X	X	X
Blood Pressure and Pulse	X^2	X	X	X	X	X
Lesion Counts	X^2	X	X	X	X	X
Cutaneous Tolerability Evaluation	X^2	X	X	X	X	X
Instruct on Study Drug Application and Provide Subject Instructions	X					
Record application areas since last visit		X	X	X	X	X
Study Drug Dispensed/Retraining on mixing and application	X	X	X	X	X	
Study Drug Collected		X	X	X	X	X
Subject Study Drug Use Reviewed		X	X	X	X	X
Concomitant Medications	X	X	X	X	X	X
Adverse Events	X	X	X	X	X	X

¹Data for the Baseline Visit for this study will be the Week 12 data from the Phase 3 pivotal study for completing, eligible subjects.

²Demographics and assessments from the Week 12 visit from the preceding Phase 3 study including the physical examination, blood pressure and pulse, UPT, tolerability, and lesion counts do not need to be repeated.

³All visit dates are in reference to Baseline, e.g., Visit 2 occurs four weeks (28 days) after Baseline visit.

⁴ All Week 40 procedures should be completed for subjects who prematurely discontinue.

4.1.1 BASELINE

The following procedures were performed as Week 12 assessments in NI-AC301 or NI-AC302 and will be used for baseline values for this study:

- 1. Collect blood pressure and pulse rate after the subject has been sitting quietly for 5 minutes.
- 2. Perform a brief physical examination.
- 3. Obtain pregnancy test (WOCBP only) and evaluate results. If pregnancy test is positive, the subject may not participate in the study.
- 4. Perform Cutaneous Tolerability Evaluation on the face only.
- 5. Perform lesion counts on the face only. Inflammatory and non-inflammatory lesion counts will be performed on the entire face and reported separately.

The following procedures must be performed and recorded at the Baseline visit:

- 1. Review study procedures and information regarding the study including the potential risk and benefits of SB204 with the subject and obtain written informed consent/assent.
- 2. Review subject's concomitant medication information.
- 3. Verify appropriate contraception being used for WOCBP per Section 6.4.
- 4. Review prohibited medications, acne treatments, and supplements that should not be used during the trial.
- 5. Confirm subject meets eligibility criteria.
- 6. Dispense subject diary and study drug. Instruct subject on dispensing, mixing, and application of study product and diary completion.
- 7. Collect AEs related to study procedures performed since signing of informed consent.
- 8. Confirm the study schedule with the subject.

4.1.2 WEEKS 4, 12, 24 AND 36 (DAYS 28, 84, 168, 252)

The following procedures must be performed and recorded at the Weeks 4, 12, 24, and 36 visits:

- 1. Update concomitant medication information.
- 2. Update AE information and record any new AEs if applicable.
- 3. Obtain UPT (WOCBP only) and evaluate results.
- 4. Collect blood pressure and pulse rate after the subject has been sitting quietly for 5 minutes.

- 5. Perform cutaneous tolerability evaluation (face only).
- 6. Perform lesion counts (face only).
- 7. Record areas treated since last visit (face, upper back, upper chest/shoulders).
- 8. Collect returned study drug and diary, perform accountability, and review study drug compliance with subject.
- 9. Review subject diary for completion.
- 10. Dispense new study drug and diary.
- 11. Review and confirm the study schedule with the subject.

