	Subjects will be assessed at each visit through Week 40 for cutaneous tolerability on the face. Tolerability will be assessed on a scale of 0 to 3 where 0=none, 1=mild, 2=moderate, and 3=severe for erythema, scaling, dryness, pruritus, and burning/stinging. The body surface area (BSA) treated (based on locations) will be collected at each visit for each subject Extent of exposure will be calculated for each subject based on the number of treatments and treatment area. Extent of exposure will also be summarized on a unit day which will be defined as total exposure divided by the total number of days enrolled.
Endpoints	Safety endpoints will include adverse events, changes in physical
	examination and changes in vital sign measurements. Any clinically significant changes noted during the physical exam as well as from the vital sign measurements will be recorded as adverse events and included in the comparison. Urine pregnancy tests in women of child-bearing potential will be conducted at each visit.
	Tolerability endpoints will include the investigator's assessment of erythema, scaling, dryness, and the subject's report of pruritus and burning/stinging based on the preceding 24 hours.
Statistical Methods	All statistical processing will be performed using statistical analysis software (SAS®) unless otherwise stated. Safety analyses will be performed using the safety population.
	Safety Analyses
	Adverse Events
	All AEs occurring during the study will be recorded and classified on the basis of the Medical Dictionary for Regulatory Authorities (MedDRA) terminology. Descriptions of AEs will include the date of onset, the date the AE ended, the severity of the AE, the relationship to study medication, and the outcome. All reported AEs that occurred on or after the Baseline date will be included in the summaries and analysis. Summaries will be presented to describe the characteristics of the adverse events reported and will include the number and percentage of subjects who report at least one AE and the number of events reported by severity, seriousness, and relationship to study medication. A
	summary of adverse event system organ class (SOC) and preferred terms (PTs) will also be presented. A subject will be counted only once under

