application-site reactions may occur due to the active agent (NVN1000) or the vehicle. In other development programs, local application-site reactions that led to treatment discontinuations were observed following application of alcoholic NVN1000 Gel or Vehicle Gel under occlusion in subjects with psoriasis or to the genital/perianal area in subjects with genital/perianal warts.

Based on available data, Novan anticipates that the risks to subjects enrolling in this Phase 3 study at which the maximum strength of SB204 will be 4% once daily on up to 17% body surface area are minimal, and that appropriate monitoring is in place to assess safety. Some subjects may have a clinical benefit in this long-term, open label study.

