3.4 DOSAGE/DOSE REGIMEN

SB204 will be dispensed from a dual-chamber pump designed to deliver approximately equal amounts of NVN1000 Gel and hydrogel. NVN1000 Gel will be opaque and the hydrogel will be clear. The subject will instantly mix the two substances in the palm of the hand and then immediately massage a thin layer over the acne affected areas once daily after washing. The product should be mixed for about 5 seconds until thoroughly combined with a uniform opaque appearance then applied with the fingertips. Subjects should apply SB204 prior to bedtime.

Up to 2.7 g of SB204 4% will be applied evenly over the acne affected area, including the face, chest, back, and upper shoulders once a day for a period of up to 40 weeks (280 days). The amount of SB204 per application will vary depending on the areas to be treated as shown in Table 1 below. One pump stroke (0.9 g) will be used for the face. Application to the face, upper back and upper chest/shoulders will require up to 2.7 g (three (3) pump strokes).

Table 1: Dosing Amount by Area

Area (BSA)	Number of Pump Strokes	Amount of Product	
Face (3%)	1	0.9 g	
Upper Back (6%)	1	0.9 g	
Upper Chest/Shoulders (8%)	1	0.9 g	

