4.2 TOLERABILITY ASSESSMENTS

The evaluator will assess the subject's face at baseline and each study visit. The cutaneous tolerability scores from Week 12 of NI-AC301 or NI-AC302 will be the subject's baseline tolerability. The cutaneous tolerability assessment should be performed at least 30 minutes after study drug application. Cutaneous tolerability evaluations will include erythema, scaling, dryness, pruritus and burning/stinging. Pruritus and burning/stinging will be based on the subject's report for the previous 24 hours. Cutaneous tolerability endpoints will not be reported as an AE unless they reach severe and/or result in subject's discontinuation from the study. Subjects who develop intolerance to the product as defined by scores of 3 (severe) on two or more categories of tolerability (erythema, scaling, dryness, pruritus, burning/stinging) shall be discontinued from the study. Cutaneous tolerability assessments will be performed according to the following scales:

Erythema

Score Description

0-None No evidence of erythema present

1-Mild Slight pink coloration

2-Moderate Definite redness

3-Severe Marked erythema, bright red to dusky dark red in color

Scaling

ScoreDescription0-NoneNo scaling

1-Mild Fine scales present to limited areas of the face, barely perceptible

2-Moderate Fine scale generalized to all areas of the face

3-Severe Scaling and peeling of skin over all areas of the face

Dryness

ScoreDescription0-NoneNo dryness

1-Mild Slight but definite roughness

2-Moderate Moderate roughness 3-Severe Marked roughness

Pruritus

Score Description
0-None No itching

1-Mild Slight itching, not very bothersome

2-Moderate Moderate amount of itching, somewhat bothersome

3-Severe Severe amount of itching, definite discomfort and sleep may be disturbed

Burning/Stinging

Score Description

0-None No burning/stinging

1-Mild Slight warm, burning/stinging sensation; not very bothersome

2-Moderate Definite warm, burning/stinging sensation that is somewhat bothersome

3-Severe Hot, tingling/sensation that has caused definite discomfort and may have

disturbed sleep

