### 4.4 Extent and Duration of Exposure

Summaries of the duration of exposure, days of exposure, and extent of exposure (calculated total grams) to study drug will be presented, overall and by whether previously randomized to SB204 (SB204 experienced) or randomized to Vehicle (SB204 naïve). This information plus study drug management details will be listed as well. All exposure endpoints will take into account whether the subject received SB204 in the previous study (NI-AC301 or NI-AC302).

Duration of exposure will be defined as:

Date of Last Drug Administration – Date of First Drug Administration + 1 day

Where date of first drug administration is the date of first treatment in the previous pivotal study for subjects randomized to SB204 in the previous study, and date of first dose in the LTS for subjects randomized to vehicle in the previous study.

Days of exposure will be defined as the total number of days that the subject reported taking study medication, and includes the days of exposure to SB204 in the previous study (NI-AC301 or NI-AC302) if applicable.

Extent of exposure will be based on the number of areas treated (face, upper back, and/or upper chest/shoulders, and any other areas reported) and the number of days with treatment. For subjects randomized to SB204 in the previous studies, drug was only applied to the face so for the days of exposure from the previous studies, it will be assumed that there is only one area of application, i.e. the face.

Each application is equal to 0.9 g. Extent of exposure is estimated as the sum of application areas (face only=1, face and chest=2, etc.) times the number of days of application to those areas times 0.9g. For example, a subject who applies 200 applications to the face only will have extent of exposure = 180g, while a subject who applies 100 applications to the face and 50 applications to the upper back will have extent of exposure = 135 g. The maximum extent of exposure would be: [0.9 grams x number of days on treatment in previous study] + [0.9 grams x 4 areas x number of LTS days on treatment]. Most subjects will have less exposure than this, so extent of exposure will be categorized logically depending on actual distribution of subjects. Initially, quartiles will considered.

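### Tolerability is scored on the face only and the AE exemption names no body site, so mild or moderate local reactions on the trunk may go unrecorded at some sites and unlocated at others

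*Protocol*

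**What the plan says.** **Where drug goes.** Protocol 3.4, Table 1, gives BSA values of 3% for the face, 6% for the upper back and 8% for the upper chest/shoulders. Protocol 1.5 judges the risks of "4% once daily on up to 17% body surface area are minimal". In the pivotal studies, according to SAP 4.4, "drug was only applied to the face".

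**Where tolerability is scored.** The Baseline instruction in Protocol 4.1.1 is "Perform Cutaneous Tolerability Evaluation on the face only". Protocol 4.1.2 (Weeks 4 to 36) and 4.1.3 (Week 40/ET) use the same form: "Perform cutaneous tolerability evaluation (face only". The synopsis agrees, and Protocol 4.2 opens with "The evaluator will assess the subject's face at baseline and each study visit". No SAP shell or listing holds a tolerability score for another site.

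**What becomes an AE.** Protocol 4.2 then states: "Cutaneous tolerability endpoints will not be reported as an AE unless they reach severe and/or result in" discontinuation. That sentence names no body site. Nor do the endpoint definitions in Protocol 3.1.2 and SAP 2.2, which list erythema, scaling, dryness, pruritus and burning/stinging. Protocol 6.2 requires every AE that the subject reports to be recorded.

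**What the analysis is meant to show.** Protocol 7.7 summarises AEs by extent of exposure to look for a signal from duration or from the total body area treated. SAP 4.5.1 carries this out by duration windows and by categories of grams.

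**The concern.** On the face the exemption has a clear purpose: the 0 to 3 score takes the place of an AE record. On the trunk there is no score. If the exemption is applied there too, a mild or moderate reaction leaves no trace in the data.

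The trunk is also where this study adds most to the Phase 3 experience, because the pivotal studies treated only the face. Protocol 1.5 names erythema, scaling, dryness and burning/stinging as known application-site reactions, so the exempted findings are the expected ones. At stake is whether a long-term safety study can describe local tolerability at the newly treated sites, and whether its comparison by treated area is fair for below-severe local reactions.

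**Working it through.** **Step 1. Reproduce the plan's figure.** Table 1 of Protocol 3.4: 3 + 6 + 8 = 17, which matches the 17% in Protocol 1.5.

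**Step 2. Share of treated skin that is not scored.** Formula: (treated BSA − 3) / treated BSA, for a subject who treats the face.

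| Areas treated | Treated BSA | Not scored | Share |
|---|---|---|---|
| Face only | 3 | 0 | 0% |
| Face + upper back | 9 | 6 | 66.7% |
| Face + upper chest/shoulders | 11 | 8 | 72.7% |
| All areas | 17 | 14 | 82.4% |

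The last row is a maximum. Drug goes on acne-affected areas, and neither document forecasts how many subjects will treat the trunk.

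**Step 3. Follow each kind of finding through the two readings of Protocol 4.2.**

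| Finding | Scored? | Exemption read literally (any site) | Exemption read as facial-only |
|---|---|---|---|
| Mild/moderate, face | Yes | Not an AE | Not an AE |
| Mild/moderate, trunk | No | Not an AE: recorded nowhere | AE, no location field |
| Severe or leading to discontinuation, trunk | No | AE | AE |
| Systemic event | Not applicable | AE | AE |

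Only the second row is affected. Protocol 7.9 plans about 100 sites, so both readings could be in use at once. Trunk AE counts would then differ between sites for reasons unrelated to the drug.

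**Step 4. Check the location data.** The AE items listed in Protocol 4.3.1 are onset, end, severity, relationship, therapy and action taken. Neither these nor the columns of SAP Listing 16.2.8.1 include a body site. Even under the facial-only reading, a trunk reaction can be tied to a treated area only if the reported term happens to name it.

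**Step 5. Check the backstops.** The AE question in Protocol 6.2 is open and does not ask about treated areas. Protocol 4.3.2 provides one physical examination after Baseline, at Week 40/ET, and only clinically significant changes become AEs. Neither would reliably pick up mild or moderate trunk reactions between visits.

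**Step 6. Check the planned area analysis.** SAP 4.4 computes grams as 0.9 × areas × days.

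- Face only for 270 days: 0.9 × 1 × 270 = 243 g.
- Three areas for 90 days: 0.9 × 3 × 90 = 243 g.

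Both fall in the >100–330 g category of the shells, so grams mix area with duration. No table shows application-site AEs by area.

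**Direction of bias.** Subjects who treat more areas have more skin on which a local reaction can occur, and the additional reactions are the ones at risk of going unrecorded. Where the exemption is read literally, this pulls any comparison by area toward no signal.

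**The case against.** The facial-only reading of Protocol 4.2 is a natural one. The section opens with the face, its scaling anchors describe the face, and the word severe points to a score that exists only there. A trunk reaction would then be an ordinary AE under Protocol 6.1 and 6.2, with AEs updated at every visit. This stands as a plausible reading, so a reader who infers that trunk reactions are neither scored nor AEs goes further than the text allows. What remains is that no passage states the limit, and that this reading still yields AEs without a location.

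A reader might also infer that 82% of treated skin has no safety data, or that Protocol 7.7 cannot be answered. Neither is supported. The 82% is a share of skin area for a subject treating everything, not a share of reactions missed or of subjects affected. Protocol 7.7 covers all AEs, and capture of the systemic risks named in Protocol 1.5 (hypotension, headache) does not depend on facial scoring.

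Trunk use is not new to the programme. Protocol 1.4 describes an 18-subject cross-over study of the 8% strength on about 17% BSA, with one withdrawal for contact dermatitis whose treatment and site are not given. That is some experience, but it is small.

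Finally, face-only scoring is consistent throughout and matches the facial Week 12 baseline. With no trunk baseline listed, trunk shift tables could not be built. This is a fair reason not to ask for full trunk scoring, and the fix below does not ask for it.

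**Conclusion.** The concern holds as a recording gap confined to mild and moderate local reactions away from the face. Depending on how a site reads Protocol 4.2, these are either recorded nowhere or recorded as AEs without a location. The Protocol 7.7 question about treated area is weakened for such reactions, and biased toward no signal to the extent that sites take the literal reading.

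The unscored share is at most 14 of 17 BSA points, and zero for a face-only user. The number of reactions that would be lost cannot be estimated, because the documents give neither the expected proportion treating the trunk nor a reaction rate there. The conclusion rests on two things: the wording of 4.2 as it stands, and the assumption that at least some sites would apply it beyond the face. It is a cheap improvement, not a flaw that undermines the study.

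**What to change.** 1. In Protocol 4.2, state that the AE exemption covers only the scored facial findings.
2. Record local reactions at any other treated area as AEs, with a body-location field. Add that field to the items in Protocol 4.3.1 and to SAP Listing 16.2.8.1.
3. In the SAP, add one table of application-site AEs by area, with subjects treating that area as the denominator. Treated areas are already recorded at each post-baseline visit. Protocol 4.1.2 records upper chest/shoulders as one area while SAP Listing 16.2.6 splits them, so the table needs one agreed set of categories.
4. Show the non-facial local reactions separately from the overall AE-by-grams tables, or present those tables also with these reactions excluded. Mild trunk reactions would count as AEs while mild facial ones would not, so AE incidence would otherwise rise with treated area through the recording rule alone.

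**Cost:** a sentence in the protocol, one data field, one table and more AE records. No new visit, assessor or procedure is needed.
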